4.6.2. Adverse Events

All adverse events will be classified by System Organ Class (SOC) and Preferred Term (PT) according to the Medical Dictionary for Regulatory Activities. Selected notable AEs of interest may be reported using high-level terms or Standardized Medical Dictionary for Regulatory Activities Queries. As an example, 'renal safety event', defined in the protocol as an AE of interest, is defined by the high-level group term 'Renal disorders (excl nephropathies)'. Please refer to Section 6.3 for the SMQs of interest.

A treatment-emergent AE (TEAE) is defined as an AE that meets any of the following conditions:

- begins on or after the first dose of study intervention
- begins before the first dose of study drug and worsens in severity on or after the first dose of study drug
- is completely missing an onset date and end date
- is completely missing an onset date and the end date is on or after the first dose of study intervention.

An overview summary of the number and percentage of participants with any TEAE, serious TEAE, study drug-related TEAE, study drug-related serious TEAE, TEAE leading to treatment discontinuation, TEAE leading to study termination, and AE leading to death will be provided. The number of events will also be summarized.

Local Adverse Events (i.e., injection site reactions) will be tabulated separately in addition to the overall TEAE tables.

Summaries of the total number of TEAEs and the number and percentage of participants with at least one TEAE will be provided. The number and percentage of participants and the number of events will also be presented by SOC and PT. At each level of participant summarization, a participant is counted once if the participant reported one or more events. Percentages will be calculated out of the number of participants in the SS. The number of events at each level of SOC and PT will also be summarized.

A summary of TEAEs will also be presented in descending order from the SOC with the highest total incidence (that is, summed across treatment group) to the SOC with the lowest total incidence. If the total incidence for any two or more SOCs is equal, the SOCs will be presented in alphabetical order. Within each SOC, the PTs will be presented in alphabetical order.

A summary of AEs where the answer to "*Outcome*" is "*Fatal*" will be presented in a table. At each level of participant summarization, a participant is counted once if the participant reported one or more events. Percentages will be calculated out of the number of participants in the Safety set within the subgroup category.

A summary of TEAEs with a study intervention action taken of "*Drug Withdrawn*" will be presented in a table. At each level of participant summarization, a participant is counted once if the participant reported one or more events. Percentages will be calculated out of the number of participants in the Safety set within the subgroup category.

A summary of TEAEs which are linked to study discontinuation via the "Disposition Event: Treatment Phase" CRF page will be presented in a table. At each level of participant summarization, a participant is counted once if the participant reported one or more events. Percentages will be calculated out of the number of participants in the Safety set within the subgroup category.

A summary of TEAEs by severity will be presented in a table. The severity that will be presented represents the most extreme severity captured on the CRF page. The possible severities are *"Mild," "Moderate," and "Severe."* In the TEAE severity table, if a participant reported multiple occurrences of the same TEAE, only the most severe will be presented. Treatment-emergent AEs that are missing severity will be presented in tables as *"Severe"* but will be presented in the data listing with a missing severity. Percentages will be calculated out of the number of participants in the Safety set.

A summary of TEAEs by relationship (i.e., "*Related*" and "*Not Related*") to study drug will be presented in a table by incidence of occurrence. The investigator will provide an assessment of the relationship of the event to the study drug. The possible relationships are "*Not Related*", "*Related*". Treatment –emergent AEs that are missing a relationship will be presented in the summary table as "Related" but will be presented in the data listing with a missing relationship. Percentages will be calculated out of the number of participants in the Safety set.

The seriousness of an AE should be assessed by the Investigator independently from the severity of the AE. A serious AE (SAE) is defined as any untoward medical occurrence that at any dose results in death, is life-threatening, is a congenital anomaly/birth defect, requires in-patient hospitalization or prolongation, or results in significant disability/incapacity.

Important medical events that may not result in death, be life-threatening, or require hospitalization may be considered SAEs when, based upon medical judgment, they may jeopardize the participant and may require medical or surgical intervention to prevent one of the outcomes listed above.

Serious treatment-emergent adverse events (SAEs) will be presented in a table. Treatmentemergent SAEs by relationship to study drug will be presented in a table. A treatment-related treatment-emergent SAE is a treatment-emergent SAE with the answer "Yes" to the question "Is this event related to study treatment?" on the SAE CRF page. Treatment-emergent SAEs that are missing a relationship will be presented in the table as "Related" but will be presented in the data listing with a missing relationship. At each level of participant summarization, a participant is counted once if the participant reported one or more events. Percentages will be calculated out of the number of participants in the Safety set.

The treatment-emergent SAE data will be categorized and presented by SOC and PT in a manner similar to that described for TEAEs.

The number and percentage of participants who prematurely discontinue the study due to an AE will be summarized using MedDRA PT nested within SOC. Events will be ordered by decreasing

frequency within SOC. A listing of all the discontinuation from Study due to Adverse Event will be provided.

The number and percentage of participants who prematurely discontinue study drug due to an AE will be summarized using MedDRA PT nested within SOC. Events will be ordered by decreasing frequency within SOC. A listing of all the discontinuation from Study Treatment due to Adverse Event will be provided.

All participants who have an AE related to study treatment with an outcome of "Death Related to Adverse Event" will be presented in a listing. The listing will include patient identification including the treatment, site number, date of death, age at the time of enrollment, gender, MedDRA PT of associated AE, time from first dose of study drug to death, time from last dose of study drug to death (if patient had discontinued study drug), cause of death as reported by investigator, cause of death as adjudicated by Clinical Endpoint Committee (CEC).

Patient narratives will be provided for all patients who experience any of the following "notable" events:

- Deaths
- SAEs
- Pregnancy
- Permanent Discontinuations of study treatment due to AEs

All AEs will be presented in a listing.

Handling of missing TEAE start and end dates:

For the purpose of inclusion in TEAE tables, incomplete AE onset and end dates will be imputed as follows:

Missing onset dates (where UK and UKN indicate unknown or missing day and month respectively):

- UK-MMM-YYYY: If the month and year are different from the month and year of the first dose of study drug, assume 01-MMM-YYYY. If the month and year are the same as the first dose of study drug month and year, and the end date (after any imputation) is on or after the first dose of study drug, then assume the date of the first dose of study drug. If the month and year are the same as the first dose of study drug month, and year and the end date (after any imputation) is prior to the first dose of study drug, then assume the end date for the onset date.
- DD-UKN-YYYY/UK-UKN-YYYY: If the year is different from the year of first dose of study drug, assume 01-JAN-YYYY of the collected year. If the year is the same as the first dose of study drug year, and the end date (after any imputation) is on or after the first dose of study drug, then assume the date of the first dose of study drug. If the year is the same as the first dose of study drug, and the end date (after any imputation) is prior to the first dose of study drug, then assume the end date (after any imputation) is prior to the first dose of study drug, then assume the end date for the onset date.

Missing end dates (where UK and UKN indicate unknown or missing day and month respectively):

• UK-MMM-YYYY: Assume the last day of the month.

• DD-UKN-YYYY/UK-UKN-YYYY: Assume 31-DEC-YYYY.

4.6.3. **Product Complaints**

A product complaint is any written, electronic, or oral communication that alleges deficiencies related to the identity, quality, durability, reliability, safety, effectiveness, or performance of a study intervention. When the ability to use the study intervention safely is impacted.

Product complaints related to study interventions used in clinical studies are collected in order to ensure the safety of participants, monitor quality, and to facilitate process and product improvements.

Investigators will instruct participants to contact the site as soon as possible if he or she has a product complaint or problem with the study intervention so that the situation can be assessed.

An event may meet the definition of both a product complaint and an AE/SAE. In such cases, it should be reported as both a product complaint and as an AE/SAE.

A listing of all device product complaints, inclusive of device product complaints that lead to an AE or that could have led to an SAE had intervention not been taken will be provided. Additional summaries will be provided as deemed appropriate.

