Visit Interval Tolerance (Days)	+3/-7	0	±3	±3	±3		Flexibility is built into the screening visit to ensure adequate CGM session and appropriate timing for stopping the baseline GLP-1 RA and initiating tirzepatide at Visit 2; see Section 4.1.1.
Fasting Visit		Х			Х	Х	
Study intervention injection training with demo device		Х					Train participant with demo device prior to initial injection.
Review hypoglycemic events collected in the diary		Х	Х	Х	Х	Х	
Participant Diary							
Participant diary dispensed	Х	Х	Х	Х			Diary includes blood glucose values, collection of intervention administration, information on dosing date/time, and hypoglycemia. See Section 8.1.
Diary compliance check		Х	Х	Х	Х	Х	
Diary return		Х	Х	Х	Х	Х	
Laboratory Tests and Sample Collections							
Hematology	Х						
Hemoglobin A1C (HbA1c)	Х	Х	Х	Х	Х	Х	

GPIL	
l	
I8F-N	

Study 18F-MC-GP1L	Period I -   Screening	Period II -	Treatment	Period			Comments
Visit Number	1	2	3	4	5	ED	ED = carly discontinuation
Week Relative to Study Intervention Start	-3	0	4	8	12		
Visit Interval Tolerance (Days)	+3/-7	0	±3	士3	±3		Flexibility is built into the screening visit to ensure adequate CGM session and appropriate timing for stopping the baseline GLP-1 RA and initiating tirzepatide at Visit 2; see Section 4.1.1.
Fasting Visit		Х			Х	Х	
Clinical chemistry	Х	Х			Х	Х	Includes glucose testing.
Lipid panel		Х			Х	Х	
Urinalysis	Х						
Serum pregnancy	Х						Only for WOCBP and females with a history of tubal ligation. See Section 10.4.2.
Urine pregnancy (local)		Х			Х	Х	Collect for WOCBP only. The result must be available prior to first dose of intervention. Perform additional pregnancy tests if there is clinical suspicion of pregnancy, or as required by local law or regulation.
Follicle stimulating hormone (FSH)	X						Optional; perform as needed to confirm postmenopausal status. See Section 10.4.
Calcitonin	Х						

ЪЦ
Ģ
1Ċ
[8F-N

Study I8F-MC-GPIL	Period I - Screening	Period II -	Treatment	Period			Comments
Visit Number	1	2	3	4	5	ED	ED = early discontinuation
Week Relative to Study Intervention Start	-3	0	4	8	12		
Visit Interval Tolerance (Days)	+3/-7	0	±3	±3	±3		Flexibility is built into the screening visit to ensure adequate CGM session and appropriate timing for stopping the baseline GLP-1 RA and initiating tirzepatide at Visit 2; see Section 4.1.1.
Fasting Visit		Х			Х	Х	
Estimated glomerular filtration rate (eGFR)	Х						Calculate using CKD-EPI method.
Urinary albumin/creatinine ration (UACR)	Х						

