### **Medical conditions**

- 10. Have T1D.
- 11. Have a history of chronic or acute pancreatitis any time prior to Visit 1.
- 12. Have a clinical history of
  - o proliferative diabetic retinopathy
  - o diabetic maculopathy, or
  - nonproliferative diabetic retinopathy that requires acute treatment.
- 13. Are at high risk for CVD in the investigator's opinion or have a history of any of these CV conditions within 60 days prior to Visit 1:
  - myocardial infarction
  - percutaneous coronary revascularization procedure
  - o carotid stenting or surgical revascularization
  - nontraumatic amputation
  - o peripheral vascular procedure (e.g., stenting or surgical revascularization)
  - o cerebrovascular accident (stroke), or
  - hospitalization for congestive heart failure.
- 14. Have NYHA Functional Classification Class IV congestive heart failure.
- 15. Have a history of ketoacidosis or hyperosmolar state or coma.
- 16. Have a history of severe hypoglycemia or hypoglycemia unawareness within the 6 months prior to Visit 1.
- 17. Have a known clinically significant gastric emptying abnormality, for example, severe diabetic gastroparesis or gastric outlet obstruction.
- 18. Have undergone or plan to have during the course of the study gastric bypass (bariatric) surgery or restrictive bariatric surgery (for example, Lap-Band®), or chronically take drugs that directly affect GI motility.
- 19. Have acute or chronic hepatitis, signs and symptoms of any liver disease other than NAFLD, or ALT level >3.0 times the ULN for the reference range, as determined by the central laboratory at study entry. Participants with NAFLD are eligible to participate if their ALT level is ≤3.0 times the ULN for the reference range.
- 20. Have an estimated glomerular filtration rate <30 mL/min/1.73 m^2, or lower than the country-specific threshold for discontinuing metformin therapy (if used) or SGLT-2i (if used) per local label, calculated by Chronic Kidney Disease-Epidemiology equation by the central laboratory at Visit 1.
- 21. Have evidence of a significant, uncontrolled endocrine abnormality, for example, thyrotoxicosis or adrenal crises, in the opinion of the investigator.
- 22. Have family or personal history of MTC or MEN2.
- 23. Have a serum calcitonin level of  $\geq$  35 ng/L, as determined by central laboratory at Visit 1.
- 24. Have known or suspected hypersensitivity to study product(s) or related products.

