# 8.2.5. Clinical Safety Laboratory Tests

See Section 10.2, Appendix 2 for the list of Clinical Laboratory Tests to be performed and the SoA (Section 1.3) for the timing and frequency.

The investigator must review the laboratory results, document this review, and report any clinically relevant changes occurring during the study as an AE.

The laboratory results must be retained with source documents unless a Source Document Agreement or comparable document cites an electronic location that accommodates the expected retention duration.

Clinically significant abnormal laboratory findings are those which are not associated with the underlying disease, unless judged by the investigator to be more severe than expected for the participant's condition.

All laboratory tests with values considered clinically significantly abnormal during participation in the study should be repeated until the values return to normal or baseline or are no longer considered clinically significant by the investigator or medical monitor.

- If such values do not return to normal or baseline within a period of time judged reasonable by the investigator, the etiology should be identified, and the sponsor notified.
- All protocol-required laboratory assessments, as defined in Section 10.2, Appendix 2, must be conducted in accordance with the SoA (Section 1.3), standard collection requirements, and laboratory manual.

If laboratory values from non-protocol-specified laboratory assessments performed at an investigator-designated local laboratory require a change in participant management or are considered clinically significant by the investigator, for example, SAE or AE or dose modification, then report the information as an AE.

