#### 8.3.3.3. Renal Safety

Renal safety will be assessed based on repeated renal functional assessment as well as assessment of AEs suggestive of acute or worsening of chronic renal disease.

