6.3. Appendix 3: Search Criteria for Standardized MedDRA Queries

The Standardized MedDRA Queries of interest are listed as follows:

- Systemic hypersensitivity and anaphylactic reactions:
 - Anaphylactic reaction (SMQ), narrow search
 - Hypersensitivity (SMQ), narrow search
 - Angioedema (SMQ), narrow search
 - Severe cutaneous adverse reactions (SMQ), narrow search
- Hepatic disorders (SMQ)
- Gallbladder related disorders (SMQ)
- Acute pancreatitis (SMQ)
- Cardiac arrythmias (SMQ)

CONFIDENTIAL

• Biliary disorders (SMQ)

The search criteria for each of the SMQs are stored in PPD Biostatistics Technology Infrastructure (BTI) in:

\\wilbtib\wilbtia00\Global Bios Library\Dictionaries\MedDRA\Current\MedAscii\smq_list.asc

7. References

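### The SAP defines the renal safety event by a group term that excludes nephropathies by name, which is narrower than the protocol's renal topic; no other renal search fills the gap

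*SAP*

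**What the plan says.** Protocol 8.3.3.3 (Renal Safety), one of the safety topics of special interest, rests on two sources: repeated tests of renal function, and "assessment of AEs suggestive of acute or worsening of chronic renal disease". No type of renal disease is carved out.

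SAP 4.6.2 (Adverse Events) refers back to that topic. It describes the "renal safety event', defined in the protocol as an AE of interest", and says that it "is defined by the high-level group term 'Renal disorders (excl nephropathies". No second category is added.

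SAP 6.3 (Appendix 3) opens its list with "The Standardized MedDRA Queries of interest are listed as follows". The list covers hypersensitivity-type reactions and hepatic, gallbladder, pancreatitis, arrhythmia and biliary events. It has no renal entry.

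**The concern.** The protocol sets the scope of the renal topic and the SAP should carry that scope into a search. Here the search is narrower than the scope, and the SAP does not say so: its Introduction and section 4.9 both report no change to the analyses the protocol planned.

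The gap is relevant to this population. All participants have type 2 diabetes. The renal exclusion in Protocol 5.2 (criterion 20) reads "Have an estimated glomerular filtration rate <30 mL/min/1.73", with a higher local threshold where metformin or an SGLT-2 inhibitor is used, so participants can enter with chronic renal disease. Nephropathy is a direct instance of the chronic disease whose worsening the protocol wants to see. Protocol 8.3.3.2 also links severe gastrointestinal events and dehydration to declining renal function, and gastrointestinal tolerability is one of the things the trial sets out to describe. A reader who takes the renal grouping as the answer to the protocol's question could be reading an incomplete count.

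**Working it through.** No arithmetic applies: the point concerns the content of an adverse event category, and the plan gives no figure to reproduce. The check sets the sections side by side.

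1. **Scope in the protocol.** Section 8.3.3.3 covers adverse events pointing to acute renal disease or to worsening chronic renal disease. It does not name diabetic nephropathy, but worsening diabetic nephropathy is worsening chronic renal disease.

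2. **Scope in the SAP.** Section 4.6.2 uses one group term, and the exclusion of nephropathies is part of that term's name. An event coded as a nephropathy is therefore inside step 1 and outside step 2. The dictionary hierarchy is not in the documents, so this step relies on the name alone.

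3. **Is it the operative definition?** The SAP introduces the sentence as an example. The wording is nevertheless definitional, and the SAP's Revision History lists the explanation of how an adverse event of interest is defined as a key change of version 2.0. No other renal definition appears in the SAP.

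4. **Does another search restore these events to the grouping?** No. SAP 6.3 has no renal query, and the Revision History describes that section as listing every query requested for the outputs.

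5. **Where would a nephropathy-coded event still appear?** Under SAP 4.6.2 it is in the treatment-emergent tables by system organ class and preferred term, in the severity and relationship tables, in the serious event and discontinuation tables where applicable, and in the listing of all adverse events. It is missing only from the renal grouping.

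6. **Does the protocol's other source, repeated renal function, cover the gap?** In part. Under the Schedule of Activities (Protocol 1.3), clinical chemistry, which includes creatinine and urea nitrogen, is taken at Visits 1, 2, 5 and early discontinuation. SAP 4.6.4.1 summarises changes from baseline, shifts and treatment-emergent high or low values. However, eGFR (the row with the comment "Calculate using CKD-EPI method") and "Urinary albumin/creatinine ration (UACR") are marked at Visit 1 only, so neither has a scheduled post-baseline value. Albuminuria in particular has no scheduled follow-up measurement.

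7. **Size.** The same clinical event could be reported as renal impairment, renal failure or worsening chronic kidney disease, and might then fall inside the existing term. The shortfall lies somewhere between none and all of the nephropathy-type events, depending on reporter wording and coding. The documents give neither a renal event rate nor a coding mix, so it cannot be narrowed further.

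**The case against.** The strongest reply is that only a label is lost. Every event remains visible in the general tables and the listing, creatinine is analysed from measured values, and the SAP says only that selected events of interest may be reported by such groupings. The table specifications are in a separate document, so the SAP text does not itself commit to a renal table. All of this is correct and limits the point to a descriptive grouping. It does not remove the mismatch: where the grouping is used, its stated definition is narrower than the protocol's topic, and a reader would have to search the general tables to complete it.

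A reader might infer more than the documents support in four ways:

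- **That nephropathy events go unreported.** They do not; see step 5.
- **That a creatinine rise reported as an adverse event is also missed.** Protocol 8.2.5 does require investigators to "report any clinically relevant changes occurring during the study as an AE". Where the dictionary places such terms is not in the documents, and Protocol 10.3.4 asks for the diagnosis in preference to individual signs whenever possible. Measured creatinine is summarised in any case.
- **That the renal count is understated by some percentage.** No basis for such a figure exists in the documents.
- **That the lack of a control arm hides the shortfall.** A control arm would be searched with the same term and have the same gap.

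**Conclusion.** The point stands as a mismatch of definitions. As written, SAP 4.6.2 leaves an adverse event coded as a nephropathy out of the renal safety grouping, although Protocol 8.3.3.3 includes worsening chronic renal disease, and nothing in SAP 6.3 brings it back.

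The conclusion assumes that the group term means what its name says and that SAP 4.6.2 is the definition the programmers will follow. The size of the shortfall is unknown and may be zero. The effect is confined to one descriptive safety summary; the primary endpoint, alpha, power and overall adverse event counts are untouched. It should be corrected because the correction is cheap and the population is one in which nephropathy is expected, but it is not a threat to the trial's main conclusions.

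**What to change.** In SAP 4.6.2, widen the definition of the renal safety event so that it also includes nephropathy terms. Any of three routes would do: an added group term, a prespecified list of preferred terms, or a renal query covering both acute and chronic renal disease. The choice should be checked against the dictionary version in use. List the search in SAP 6.3 and report the events by preferred term within the search, so that a reader can see what each part contributes. If the exclusion is intended, give the reason in 4.6.2 and declare it in 4.9.

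The change needs SAP wording and a wider search of adverse event data that are coded anyway; it needs no new data, visits or participants. The downside is that a few less specific events will enter the grouping, which reporting by preferred term makes visible.
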